6.5 Safety Analysis

All safety analysis will be performed on the Safety population.

Potentially clinically significant (PCS) abnormalities will be defined according to the Akros Safety Reporting Standards (Standard72.doc, 10/18/2004). The PCS values for vital signs, ECG and laboratory data will be flagged in data listings.

Treatment-emergent PCS values will be summarized, presenting the number and percentage of subjects who had at least one PCS value on or after the first dose of study drug (JTE-051 or

placebo). The denominator is always the number of subjects in the safety population, regardless of whether the subject had any post-baseline measurements. The numerator is any PCS value in the treatment-emergent period if the baseline is normal or missing; and is any worsening PCS value in the treatment-emergent period if the baseline is also a PCS value. A worsening PCS is defined as a $> (<)$ 0 change from baseline if a high (low) value indicating undesirable outcome; or the PCS value is in the opposite direction of the baseline PCS value. Note that for the purpose of determining PCS abnormalities, baseline is always the last non-missing value before the first dose of study drug.

6.5.1 Adverse Events (AEs)

The number and percentage of subjects experiencing TEAEs will be tabulated by treatment according to the following categories:

- Overall summary of TEAEs.
- TEAEs by system organ class and preferred term.
- TEAEs leading to study discontinuation by system organ class and preferred term.
- TEAEs by system organ class, preferred term and AE severity.
- TEAEs by system organ class, preferred term and AE causality.
- TEAEs by preferred term (in order of descending frequency in the total JTE-051 group).
- Serious AEs (SAEs) by system organ class and preferred term.
- Serious AEs leading to study discontinuation by system organ class and preferred term.

Listings will be provided for SAEs and AEs leading to study discontinuation.

6.5.2 Medical History

Subjects with significant medical history conditions and/or surgeries, the corresponding system organ class and preferred term coded from the MedDRA (version 21.0) will be presented in the data listing.

6.5.3 Clinical Laboratory Tests

Descriptive statistics of observed results and change from baseline for hematology, coagulation, serum biochemistry, bone-specific alkaline phosphatase, lipid panel and continuous urinalysis will be presented by time point and treatment group. Frequency and percentage of the distribution of discrete urinalysis tests will be presented by time point. Number and percentage of subjects with treatment-emergent PCS abnormal values will be summarized by treatment group.

Number and percentage of subjects with post-baseline abnormalities in liver tests will be summarized by treatment group according to [Table 3](#).

Table 3. Criteria for Categorical Analysis in Liver Tests

Parameter	Specified Value			
ALT	ALT \geq ULN \times 3	ALT \geq ULN \times 5	ALT \geq ULN \times 10	ALT \geq ULN \times 20
AST	AST \geq ULN \times 3	AST \geq ULN \times 5	AST \geq ULN \times 10	AST \geq ULN \times 20
ALT and AST	ALT and AST \geq ULN \times 3	ALT and AST \geq ULN \times 5	ALT and AST \geq ULN \times 10	ALT and AST \geq ULN \times 20
ALT or AST	ALT or AST \geq ULN \times 3	ALT or AST \geq ULN \times 5	ALT or AST \geq ULN \times 10	ALT or AST \geq ULN \times 20
T-Bil	T-Bil $>$ ULN \times 1.5		T-Bil $>$ ULN \times 2	
ALP	ALP $>$ ULN \times 1.5			
ALT and T-Bil	ALT \geq ULN \times 3 and T-Bil \geq ULN \times 1.5		ALT \geq ULN \times 3 and T-Bil \geq ULN \times 2	
AST and T-Bil	AST \geq ULN \times 3 and T-Bil \geq ULN \times 1.5		AST \geq ULN \times 3 and T-Bil \geq ULN \times 2	
AT, ALP and T-Bil	ALT \geq ULN \times 3, AST \geq ULN \times 3, ALP \geq ULN \times 2 and T-Bil \geq ULN \times 2			
ALT and AST	ALT or AST $>$ ULN \times 3 at any treatment visit and any of the following AEs: Nausea, Vomiting, Anorexia, Abdominal pain or Fatigue, reported within +/- 14 days of the abnormal AT values.			

Other clinical laboratory tests (e.g., drug abuse, alcohol screen, viral serology) will be listed in the data listings.

Qualitative urine parameters are generally reported by a descriptive score, which may differ between laboratories. For pooling the data, a four-point scale is used. The five-point scale will be converted into a four-point scale by combining the lowest two positive results as shown in the table below. Furthermore, a clinical review will be performed on the mapping of the descriptive scores to the four-point scale; and the descriptive scores will be remapped where appropriate. The four-point scale will be used in the summary of the PCS abnormality analysis.

Five-point scale	Four-point scale
Negative	Negative
Trace	Rare/Mild
1+	Rare/Mild
2+	Moderate
3+	Severe

The mean profile may be presented for selected laboratory parameters.

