nonclinical and clinical data available to date. These include restrictions aiming to minimize the risk to the participating subjects, to minimize the confounding factors in the assessment process and to monitor and adequately manage any safety-related findings, as they occur. Thus, subjects at high risk of developing immunosuppression-related AEs, such as infections or malignancies, including those with pre-existing conditions (e.g., clinically-manifest or latent tuberculosis, active infections with hepatitis B or C viruses or the human immunodeficiency virus [HIV] infection) or significant hematological abnormalities (see Exclusion Criterion # 3) are excluded from participating in the study.

[REDACTED]
[REDACTED] Other, general safety-related restrictions, such as cardiovascular-system-related, hepatic and renal function-related restrictions have been implemented, taking into account the co-administration with MTX (a medication with known significant hepatic and renal-related toxicity), as well as the known safety signals associated with other comparable compounds on the market or in development (e.g., hepatic or lipid-related signals). The procedures set in place to ensure that the appropriate subjects are randomized in this “first-in patient” POC study in subjects with RA, as well as the safety management strategies implemented in the study are discussed in the following section: “Justification for Study Design”.

Justification for Study Design

A parallel group, placebo-controlled, add-on therapy design will be employed in this study, to assess the effect of JTE-051 on the efficacy parameters and to evaluate the safety of JTE-051, compared to placebo in subjects with active RA. Briefly, upon completion of all protocol-mandated screening procedures, the qualified subjects will be randomized at Visit 2 in a 1:1:1:1:1 ratio to one of the following five parallel dose groups: JTE-051 50 mg QD, JTE-051 100 mg QD, JTE-051 150 mg QD, JTE-051 200 mg QD or placebo QD (50 subjects to be randomized per arm; see Section 3.8.1.6 for considerations related to sample size calculation), and will receive the double-blind (DB) treatment for 12 weeks followed by a four-week Follow-up Period. The single-dose AE051-U-11-001

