5.3.6 Clinical Laboratory Results

Hematology, coagulation, serum biochemistry, bone-specific alkaline phosphatase, lipid profile and urinalysis are collected as scheduled in [Table 1](#). The following information will be

derived for each of the hematology, coagulation, serum biochemistry, urinalysis and other parameters:

- Change from baseline at all post-baseline visits
- Classification relative to the normal range ('Low', 'Normal' or 'High')
- Treatment-Emergent potentially clinically significant (PCS) abnormalities, if applicable

Abnormalities in liver tests will be identified.

In addition, 25-hydroxyvitamin D, rheumatoid factor (RF), anti-cyclic citrullinated peptide (anti-CCP) antibodies and serum immunoglobulins G, M and A (IgG, IgM and IgA), viral serology, drugs of abuse and alcohol screen, pregnancy test and follicle stimulating hormone will also be obtained at the corresponding scheduled visit, respectively.

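### SAP Table 3 counts subjects with raised transaminase and bilirubin but cannot separate those without raised ALP, because its only three-way row requires ALP to be raised and both enzymes to be high

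*SAP*

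**What the plan says.** SAP section 6.5.3 uses Table 3 as the categorical liver summary: "Number and percentage of subjects with post-baseline abnormalities in liver tests will be summarized by treatment group according to" that table. The rows that bear on this point are:

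- **Combined row**, labelled 'AT, ALP and T-Bil': ALT and AST each at least 3×ULN, together with "ALP \geq ULN \times 2 and T-Bil \geq ULN \times 2".
- **ALT and T-Bil row**: "ALT \geq ULN \times 3 and T-Bil \geq ULN \times 2", with a second cell at bilirubin 1.5×ULN.
- **AST and T-Bil row**: "AST \geq ULN \times 3 and T-Bil \geq ULN \times 2", again with a 1.5×ULN cell.
- **ALP row**: ALP above 1.5×ULN, on its own.
- **Last row**: "ALT or AST $>$ ULN \times 3 at any treatment visit and any of the following AEs", followed by a symptom list and a ±14-day window. It has no bilirubin or ALP condition.

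No row sets an upper limit on ALP, and no row pools ALT or AST with bilirubin. SAP section 5.3.6 adds only this: "Abnormalities in liver tests will be identified".

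The protocol names the hepatic risk. Section 1.3 cites the hepatic toxicity of the background methotrexate and "known safety signals associated with other comparable compounds on the market or in development (e.g., hepatic or lipid-related signals".

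**The concern.** A reader who sees a transaminase and bilirubin rise will next ask whether ALP rose with it. Table 3 brings ALP into a composite only once, and there it asks for ALP to be high. A subject whose ALP stays below 2×ULN therefore cannot enter that row, and no other row is reserved for such subjects.

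The combined row also needs both enzymes at 3×ULN or more. The last row uses AT to refer to either enzyme, while the row labelled 'AT, ALP and T-Bil' requires both. A subject with one enzyme raised falls out of the combined row whatever the ALP value.

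What is at stake is how well the table describes a risk the protocol itself raises. Exclusion criterion 5 removes subjects with ALT or AST above 1.2×ULN or bilirubin above 1.5×ULN at Screening. A combined rise would therefore normally be new on study and worth describing exactly.

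**Working it through.** The SAP gives no figure to reproduce here. The check is one of logic.

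**Inputs.** The row definitions come from SAP Table 3. The pattern of interest is an assumption, because neither document defines one: (ALT or AST ≥3×ULN) and T-Bil ≥2×ULN and ALP <2×ULN.

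**Grid (illustrative values, in ×ULN).**
- ALT and AST: 0.8, 2, 3, 5, 10, 20
- ALP: 0.8, 1.4, 1.6, 1.9, 2, 3, 5
- T-Bil: 0.8, 1.5, 1.6, 2, 2.5, 4

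Total: 6 × 6 × 7 × 6 = 1,512 combinations. Four of the six enzyme values are ≥3. So 4 × 4 = 16 of the 36 enzyme pairs have both raised, and 36 − 2 × 2 = 32 have at least one raised. Three T-Bil values are ≥2. Four ALP values are <2 and three are ≥2.

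**Counts.**

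| Set | Combinations | Within the pattern |
|---|---|---|
| Pattern of interest | 32 × 3 × 4 = 384 | 384 |
| Combined row as written | 16 × 3 × 3 = 144 | 0 |
| ALT + T-Bil ≥2 | 4 × 6 × 3 × 7 = 504 | 4 × 6 × 3 × 4 = 288 |
| AST + T-Bil ≥2 | 504 | 288 |
| Either of these two rows | 32 × 3 × 7 = 672 | 384 |

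The two pair rows together capture all 384, so nothing is lost. They also hold 672 − 384 = 288 combinations with ALP ≥2.

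**Can the pattern be recovered by subtraction?** Taking the combined row away from the two pair rows leaves 672 − 144 = 528. Of these, 528 − 384 = 144 still have ALP ≥2, because only one enzyme is raised. The table also reports the two pair rows separately. A subject with both enzymes raised is counted twice, and no row gives the overlap needed to form the union.

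**Two subjects the table cannot tell apart.** Take ALT 0.8×, AST 3×, T-Bil 2×, with ALP 1.6× in one subject and 2× in the other. Both enter AST ≥3, ALT or AST ≥3, T-Bil >1.5, ALP >1.5 and both AST + T-Bil cells. Neither enters the combined row, because ALT is low. Only the first fits the pattern.

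The ALP row helps in one situation. If it is empty for an arm, every transaminase-plus-bilirubin case in that arm has ALP at or below 1.5×ULN. Otherwise the counts do not settle the matter.

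**If the sign in the source is < rather than ≥.** The combined row would then hold 16 × 3 × 4 = 192 of the 384. The other 192, with one enzyme raised, would still be outside it.

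**After the fix.** The row equals the pattern by construction: 384 of 384 and no others.

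**The case against.** The strongest reply is that no case goes uncounted. Any subject with ALT or AST ≥3×ULN and T-Bil ≥2×ULN appears in at least one of the two pair rows, directly above the combined row. SAP section 7 lists all collected data by subject, including laboratory transfers, so in a study of about 250 subjects ALP can be looked up. This stands, and it limits the point to presentation.

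Neither document says what the combined row is for, nor mentions hepatocellular or cholestatic patterns. Every laboratory condition in Table 3 is an elevation threshold, and the table has another row requiring both enzymes. A row for subjects with all four analytes raised contradicts nothing. This also stands: the row is coherent as written, but the table has no companion row for cases without raised ALP.

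The ALP sign was read from extracted PDF text and could be a misread. That cannot be excluded. If so, only the both-enzymes point remains.

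A reader might go further and infer that Table 3 misses liver injury with jaundice, that it targets the less worrying pattern, or that every hepatocellular case is excluded. The documents support none of these. The first is contradicted by the pair rows. The second needs a clinical ranking that the documents do not give. The third depends on the definition: with an assumed ALT-to-ALP ratio of at least 5, 36 of the 144 combined-row combinations would qualify, for example ALT 10× with ALP 2×.

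**Conclusion.** The point holds as a minor gap in a descriptive safety table. The combined row cannot contain a case with ALP below 2×ULN or a case with only one enzyme at 3×ULN. The Table 3 counts cannot in general separate transaminase-plus-bilirubin rises without raised ALP from those with it. Such cases are still counted in the pair rows.

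No rate or risk bound should be attached. It is tempting to read a zero in the combined row over about 200 active subjects as an upper limit of 3/200 = 1.5%. That is not valid. The neighbouring rows would show the case, and the table is by treatment group, where the same rule would give 3/50 = 6%. The grid counts describe logical combinations and say nothing about frequency.

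The conclusion rests on two things: the inequality signs as extracted, and ALP <2×ULN as the marker of no raised ALP, which is an assumption.

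**What to change.** 1. Check the direction of the ALP inequality in the combined row against the source SAP.
2. Add one row, or correct the existing one, to read: (ALT or AST ≥3×ULN) and T-Bil ≥2×ULN and ALP <2×ULN. Have the sponsor confirm the ALP cut-off.
3. State that the values come from the same draw. The multi-analyte laboratory rows give no timing rule, whereas the last row does.
4. If the ALP ≥2×ULN row is wanted, keep it and label it as raised-ALP. State whether AT means either enzyme or both.
5. List the subjects who meet either row, with all four values.

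The cost is one table row and a short listing. ALT, AST, ALP and bilirubin are all in the serum biochemistry panel (protocol section 3.5.6.10), which Table 1 schedules at every visit. No new data are needed, and trial conduct does not change.

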6.5.4 Vital Signs

Descriptive statistics of observed results and change from baseline for vital signs and body weight will be presented by time point and treatment group. Number and percentage of subjects with treatment-emergent PCS abnormal values will be presented by treatment group.

6.5.5 12-Lead ECG

Descriptive statistics of observed results and change from baseline will be presented by time point and treatment group for RR, PR, QRS, QT and QTcF intervals. The number and percentage of subjects with treatment-emergent PCS abnormal values will be presented by treatment group. Clinical interpretation of overall ECG findings will be summarized by time point and treatment group.

6.5.6 Concomitant Medications Analysis

Prior medications and concomitant medications will be listed in the data listings. Concomitant medications will be summarized by ATC Level 3 term, drug preferred term and treatment group.

6.5.7 Study Medication Exposure and Compliance

Summary statistics will be presented for % compliance by visit and by treatment group. Summary statistics for total duration of study medication exposure and overall % compliance will be presented by treatment group.

6.6 Pharmacokinetic Analysis

6.6.1 Method of PK Data Representation

The PK data including individual data and descriptive statistics for plasma drug concentrations will be represented with 3 significant values except for CV% which will be represented to 1 decimal place. The ratio values (see Section 6.6.2) will be displayed to 2 decimal places.

6.6.2 Descriptive Statistics of Trough Plasma Concentrations

Descriptive statistics of trough plasma concentration data for JTE-051 will be presented by treatment and visit (nominal time point; week) with N, arithmetic mean, geometric mean, SD, CV%, median, minimum and maximum. The mean ratio of trough concentration relative to the lowest dose will be calculated. Mean plasma concentration-time profiles will be plotted by treatment on linear scales. Below the limit of quantification (BLQ) concentrations will be treated as zero for descriptive statistics.

6.6.3 Exploratory Exposure-Response Analysis

The relationship between JTE-051 trough concentration and ACR20 response rate will be explored based on the superimposed time course by treatment.

7. SUBJECT DATA LISTING

Subject listings of all the data collected in the study database, including eCRF data and any external data transfers (such as clinical laboratory results), will be presented by treatment group and subject number.

If a subject prematurely discontinues the study, additional subjects may be enrolled at the discretion of the Sponsor, as appropriate.

8. SOFTWARE AND QUALITY CONTROL

All analysis will be performed using SAS® Version 9.1.3 or higher. The SOPs of [REDACTED] will be followed in the creation and quality control of all tables, listings and analysis.

9. REFERENCES

Please see the references in protocol.

10. APPENDICES

10.1 Mock Summary Tables

The mock summary tables will be created in a separate document.

10.2 Mock Data Listings

The mock summary listings will be created in a separate document.

10.3 Mock Figures

The mock summary figures will be created in a separate document.
